#### **Severity Grading School for Adverse Events:**

Adverse event severity will be graded as below

Classification	Examples
Mild (Grade 1) infants are asymptomatic or have mild symptoms associated with study intervention that require clinical or diagnostic observations only; no intervention indicated.	
 
• Methemoglobinemia >2%
 
• NO2 > 1.5
 
• Hypokalemia <3
 
• Left Ventricular Dysfunction: Ejection Fraction decrease by 20%
 
• Thrombocytopenia: Platelets <100,000
 
• Hyperbilirubinemia in the absence of other known risk factors that requires single phototherapy
 
• Mild Hypotension (mean BP < # gestation weeks) that requires no treatment
 

Moderate (Grade 2) if infants have moderate symptoms that require discontinuing study intervention, non-urgent treatment or intervention	
 
• Methemoglobinemia >3%
 
• NO2 > 2
 
• Hypokalemia <2.7
 
• Left Ventricular Dysfunction: Ejection Fraction decrease by 30%
 
• Thrombocytopenia: Platelets <50,000
 

Current Version 9/10/2020  
Date:

IRBNet #: 1170748

Previous Version  
Date:

Page 20 of 25

	
 
Hyperbilirubinemia in the absence of other known risk factors that requires double phototherapy
 
Moderate Hypotension (mean BP < # gestation weeks) that requires IV fluid boluses after starting intervention
 

Severe (Grade 3): Infants developed severe or medically significant symptoms that is not immediately life threatening but require treatment or intervention.	
 
Methemoglobinemia >5%
 
NO2 > 3
 
Hypokalemia <2.5
 
Left Ventricular Dysfunction: Ejection Fraction decrease by 40%
 
Thrombocytopenia: Platelets <30,000
 
Hyperbilirubinemia in the absence of other known risk factors that requires triple phototherapy
 
Severe Hypotension (mean BP < # gestation weeks) that require single cardiotropic infusion after starting the study intervention
 

Life Threatening (Grade 4): A complication that is life threatening and requires urgent intervention	
 
Methemoglobinemia >7.5%
 
NO2 > 5
 
Hypokalemia <2
 
Left Ventricular Dysfunction: Ejection Fraction decrease by 50%
 
Thrombocytopenia: Platelets <30,000+ skin or mucosal bleeding
 
Hyperbilirubinemia in the absence of other known risk factors that requires exchange transfusion
 
Severe Hypotension (mean BP < # gestation weeks) that require multiple cardiotropic infusions after starting the study intervention
 

Death (Grade 5): Any death that is directly related to study intervention	
 
Any death that cannot be explained by the existing clinical status (Sepsis/ resistant respiratory failure etc.) and directly related to iNO toxicity (all points mentioned above)
 

Relatedness/Causality of an adverse event will be determined and classified below

Classification	Definition
Related	There is an association between the event and the administration of investigational study drug, plausible mechanisms for the event to be related to the investigational study drug and causes other than the investigational study drug have been ruled out, and/or the event reappeared on re-exposure to the investigational study drug.
Possibly related	There is an association between the event and the administration of the investigational study drug and there is a plausible mechanism for the event to be related to investigational study drug, but there may also be alternative

Current Version 9/10/2020 IRBNet #: 1170748  
Date:

Previous Version Page 21 of 25  
Date:

	etiology, such as characteristics of the subject's clinical status or underlying disease.
Unlikely related	The event is unlikely to be related to the investigational study drug and likely to be related to factors other than investigational study drug.
Not related	The event is related to an etiology other than the investigational study drug (the alternative etiology will be documented in the study subject's medical record).

All SAEs should be reported to the PI and study Coordinator within 48 hours. Deaths should be reported to the PI and study Coordinator within 24 hours. The medical monitor will then be notified and will review the event. After review, additional notifications will be made to the DSMB, IRB, and FDA as necessary. When deemed necessary by the medical monitor, the DSMB will be notified of any significant events immediately and a meeting will take place to determine appropriate actions.

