## Adverse Event Reporting

An adverse event is defined as “any untoward medical occurrence associated with the use of a drug in humans, whether or not considered drug related.”

A serious adverse event is defined as an adverse event “if, in the view of the investigator, it results in any of the following outcomes: Death, a life-threatening adverse event, inpatient hospitalization or prolongation of existing hospitalization, a persistent or significant incapacity or substantial disruption of the ability to conduct normal life functions, or a congenital anomaly/birth defect. Important medical events that may not result in death, be life-threatening, or require hospitalization may be considered serious when, based upon appropriate medical judgment, they may jeopardize the patient or subject and may require medical or surgical intervention to prevent one of the outcomes listed in this definition. Examples of such medical events include allergic bronchospasm requiring intensive treatment in an emergency room or at home, blood dyscrasias or convulsions that do not result in inpatient hospitalization, or the development of drug dependency or drug abuse.”

Adverse events that meet criteria for reporting will be submitted to the FDA and/or IRB as applicable. Given this high-risk patient population, a number of adverse events are expected. The key monitoring function will be to assess whether evidence is accruing that suggests a differential adverse event rate associated with treatment. AE's collected include elevated met hemoglobin or nitrogen dioxide, rebound pulmonary hypertension after discontinuing iNO, myocardial dysfunction/heart failure, hypotension, pulmonary hemorrhage, pneumothorax, PDA (if treated), NEC (stage 2b or 3), culture proven sepsis (treated with antibiotics  $\geq$  5 days), IVH (grade III or IV), ROP (severe), death, cardiac arrest or other life-threatening events. These adverse events will be collected from the time the subject starts intervention or placebo through the end of study participation (at 36 weeks corrected gestational age) and will be documented in the subject's chart.

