### Serious Adverse Events (SAE) and Adverse Events related to iNO Treatment:

Severe adverse events of special interest include one or any combination of the following

1. Pulmonary edema due to worsening of left ventricular dysfunction (occur when infants with pre-existing LV dysfunction are treated with iNO)

---

Current Version 9/10/2020 IRBNet #: 1170748  
Date:

Previous Version Page 19 of 25  
Date:

2. Elevated met Hb level (>5%) on 2 samples 6 hours apart or > 7.5% on a single reading
3. If nitrogen di-oxide (NO2) concentration is more than 3 ppm for 6 hours or more than 5 ppm on a single reading

Methemoglobinemia and elevated NO2 levels are dose dependent adverse events seen among infant treated with higher dose (>20ppm)

Adverse Events of Special Interest related to iNO treatment will be defined as one or any combination of the following

1. Rebound Pulmonary Hypertension Syndrome: This is seen after the abrupt withdrawal of iNO. Signs and symptoms of Rebound Pulmonary Hypertension Syndrome include hypoxemia, systemic hypotension, bradycardia, and decreased cardiac output. If Rebound Pulmonary Hypertension occurs, reinstate iNO therapy immediately.
2. Other rare adverse events may include thrombocytopenia (Platelets <50,000), hypokalemia (< 2.5 mEq/dl), hyperbilirubinemia while on study intervention (at phototherapy threshold for age and gestation) in absence of other known risk factors, atelectasis while on study intervention (as noted on chest x ray with lung collapse) and hypotension (below 5th centile for age and gestation)

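### Grade 5 is limited to treatment-caused deaths and rebound PH to stopping iNO, so read literally these two safety tallies are not valid between-arm comparisons

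*Combined protocol and SAP*

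**What the plan says.** Four parts of the protocol bear on this.

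- **Grading table** (Severity Grading School for Adverse Events). The classification column defines Grade 5 as "Any death that is directly related to study intervention". The example column adds that the infant's clinical status must not explain the death, naming sepsis and resistant respiratory failure, and that the death must be "directly related to iNO toxicity (all points mentioned above".
- **Causality.** Directly after the grades, the same section says "Relatedness/Causality of an adverse event will be determined and classified below" and gives four levels, from related to not related.
- **Rebound PH.** Adverse Event Reporting lists "rebound pulmonary hypertension after discontinuing iNO" among the collected events. The section on SAEs and AEs related to iNO treatment describes the syndrome by four signs (hypoxemia, systemic hypotension, bradycardia, decreased cardiac output), says "This is seen after the abrupt withdrawal of iNO", and attaches an instruction to restart iNO.
- **Purpose.** Adverse Event Reporting states: "The key monitoring function will be to assess whether evidence is accruing that suggests a differential adverse event rate associated with treatment". The same paragraph lists "ROP (severe), death, cardiac arrest or other life-threatening events" with no causal condition, and collection runs in both arms to 36 weeks.

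**The concern.** A severity grade should describe how bad an event was, and a relatedness scale should describe what caused it. Grade 5 mixes the two. A death with an ordinary neonatal explanation falls outside Grade 5, and Grade 4 describes a life-threatening complication rather than a death, so the scale has no place for it. The two Grade 5 columns also differ: one covers the study intervention, which could be either gas, and the other covers iNO only.

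Rebound PH has a related fault. Its definition names the active gas instead of the masked study gas. The placebo arm should supply the background rate of hypoxemia, hypotension and bradycardia when gas is weaned or stopped in these infants. Without that rate, a count in the iNO arm cannot be interpreted.

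At stake is whether these two tallies mean anything when set side by side by arm. Used literally, the Grade 5 tally could omit an excess of deaths that each had another explanation, and the rebound tally could show an excess on iNO where none exists.

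**Working it through.** The plan gives no figure to reproduce, so the main check is a comparison of definitions.

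| Event | Condition in the definition | Can an infant never exposed to iNO meet it? |
|---|---|---|
| Grade 5, classification column | Caused by study intervention | Yes, if placebo gas counts as the intervention |
| Grade 5, example column | Unexplained clinically and caused by iNO toxicity | No |
| Rebound PH, both places | Follows stopping iNO | No |
| Death as a collected AE | None | Yes |
| Grades 2 to 4 | Severity and thresholds; no attribution to iNO | Yes |

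Study Visits uses arm-neutral wording: study gas (iNO or placebo) is resumed as randomised if PH recurs in the first 2 weeks of life, and iNO or placebo is weaned in non-responders. The iNO-only wording of the rebound event is therefore out of step with the rest of the protocol.

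The plan does not say how the definitions are applied under masking. There are two possibilities.

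1. A masked assessor records the event whichever gas was stopped. The counts are then comparable, but they do not follow the written definition.
2. The definition is enforced once allocation is known. The placebo count is then 0, apart from placebo infants who received iNO.

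**Illustration of the second possibility for rebound PH.** Inputs: 34 infants per arm (Study Site(s)/Location(s) and Number of Subjects); a true rate r of rebound-like signs, equal in both arms, assumed because the documents give none; no iNO exposure in the placebo arm.

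- Expected iNO count = 34 × r.
- Two-sided Fisher p for k v 0 with equal arms = 2 × C(34,k) / C(68,k).
  - k = 5: 2 × 278,256 / 10,424,128 = 0.053.
  - k = 6: 2 × 1,344,904 / 109,453,344 = 0.025.
- So 6 is the smallest count giving p below 0.05 against 0. Its probability is P(X ≥ 6) with X binomial(34, r).

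| Assumed r, both arms | Expected iNO count | Placebo count as defined | P(6 or more on iNO) |
|---|---|---|---|
| 5% | 1.7 | 0 | 0.6% |
| 10% | 3.4 | 0 | 11.9% |
| 15% | 5.1 | 0 | 40.3% |
| 20% | 6.8 | 0 | 70.0% |

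**Illustration for Grade 5.** With assumed mortality of 10% to 20%, expected deaths per arm run from 34 × 0.10 = 3.4 to 34 × 0.20 = 6.8. If 7 infants died on iNO and 3 on placebo, each with a clinical explanation, Grade 5 would read 0 v 0. The collected AE of death would still read 7 v 3.

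**The case against.** The strongest reply is that little depends on these definitions. Death from any cause is collected in both arms, must be reported to the PI and study coordinator within 24 hours, and enters the primary endpoint with a relative risk between arms. Seriousness is defined by outcome, withdrawal by explicit criteria, and the enrollment pause by related SAEs or safety discontinuations. No stated rule or analysis uses Grade 5. This stands, and it limits the point to two tallies. One qualification is that withdrawn infants are left out of the final analysis, so for them the AE record, which continues through hospitalization, is what preserves the death count.

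A reader might infer several stronger things that the documents do not support.

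- **That the monitoring committee would not see an excess of deaths.** No section describes a grade-only table. The committee section says that safety data and AEs are reviewed at 50% enrollment, without giving the format.
- **That placebo infants can never meet the definitions.** They may receive iNO after unmasking (Mitigation of Risks) or, as non-responders, from the clinical team (Study Visits). A masked assessor also does not know the arm, and the classification column for Grade 5 can be read to cover placebo gas.
- **That one gas-attributed death in each arm would be tabulated 1 v 0.** That needs an unmasked step to remove the placebo death, and none is described.
- **That grading as a whole depends on attribution.** Grade 1 reads "infants are asymptomatic or have mild symptoms associated with study intervention", so an asymptomatic infant qualifies with no association. Most examples in Grades 1 to 4 are laboratory, echocardiographic or blood pressure criteria that apply in either arm.

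It can also be said that serial echocardiograms every 24-48 ± 12 hours to 14 days of life give PH recurrence data in both arms. They do, but recurrence on echocardiogram is not the acute syndrome that the AE describes, so it does not repair that tally.

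**Conclusion.** The point holds for two items. Grade 5 contains a causal condition that belongs on the relatedness scale, its two columns conflict, and clinically explained deaths are left without a grade. Rebound PH is worded so that, read literally, an infant never exposed to iNO cannot have it. Neither tally is a valid between-arm comparison for the monitoring purpose that the protocol sets itself.

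It does not extend to the safety comparison as a whole. The all-cause death comparison is unaffected by these definitions. So are the other listed events, such as pulmonary hemorrhage, pneumothorax, NEC, sepsis, severe IVH and severe ROP.

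The size depends on how literally the definitions are applied, which the plan does not state. Under strict application and an equal true rate of 5% to 20%, the expected rebound tally is 1.7 to 6.8 v 0. These rates are assumptions, as is the 10% to 20% mortality range. The correction should be made because the wording defeats a stated purpose and costs almost nothing to change, not because a mortality signal would be lost.

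**What to change.** 1. In the grading table, define Grade 5 as death from any cause in either arm, using the same wording in both columns. Record causality only on the four-level relatedness scale.
2. For AE recording, define rebound PH by the signs already listed for the syndrome, occurring after weaning or stopping masked study gas (iNO or placebo). Use this wording in both places where the event appears. Keep it distinct from the ordinary PH recurrence covered in Study Visits.
3. Tabulate both events by randomised arm.
4. The instruction to restart iNO attached to the rebound event and the masked iNO/placebo wording in Study Visits do not match. The sponsor must reconcile them. That is a clinical decision, and the recording change above should not be taken to settle it.

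Cost: minor protocol and CRF rewording, with no new data. More deaths will carry Grade 5, and the monitoring committee should be told to expect this.

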#### Known Safety Profile of iNO:

Controlled studies have included 325 patients on iNO doses of 5 to 80 ppm and 251 patients on placebo. Total mortality in the pooled trials was 11% on placebo and 9% on iNO. In both the NINOS and CINRG1 studies, the duration of hospitalization was similar in iNO and placebo-treated groups. From all controlled studies, at least 6 months of follow-up is available for 278 patients who received iNO and 212 patients who received placebo. Among these patients, there was no evidence of an adverse effect of treatment on the need for rehospitalization, special medical services, pulmonary disease, or neurological sequelae. In the NINOS study, treatment groups were similar with respect to the incidence and severity of intracranial hemorrhage, Grade IV hemorrhage, periventricular leukomalacia, cerebral infarction, seizures requiring anticonvulsant therapy, pulmonary hemorrhage, or gastrointestinal hemorrhage. In CINRG1, the only adverse reaction (>2% higher incidence on iNO than on placebo) was hypotension (14% vs. 11%).

Nitrogen dioxide (NO2) forms in gas mixtures containing iNO and O2. Nitrogen dioxide may cause airway inflammation and damage to lung tissues. If the concentration of NO2 in the breathing circuit exceeds 5 ppm, decrease the dose of iNO. During iNO treatment, NO2 shall be continuously monitored. Methemoglobinemia is a function of time and nitric oxide dose in neonates. The methemoglobin (MetHb) concentration and time profiles during the first 12 hours of exposure to 0, 5, 20, and 80 ppm of iNO are shown below.

---

Current Version 9/10/2020 IRBNet #: 1170748  
Date:

Previous Version Page 22 of 25  
Date:

## Safety Monitoring Plan

### Safety Monitoring

A head ultrasound will be completed prior to the initiation of the study product. As standard of care in our NICU for this population, head ultrasound will be performed for intraventricular hemorrhage (IVH) screening at approximately 7 days of life and at approximately 36 weeks corrected gestational age. or prior to discharge. Real time monitoring for NO2 will be available. Methemoglobin level will be checked within 4-8 hours from initiation of intervention and then every 24-48 hours during the intervention. In addition to the primary and secondary study outcomes, we will monitor all infants for AE's as defined above.

### Data and Safety Monitoring Board (DSMB) or Equivalent

A data safety monitoring committee (DSMC) will be established for this trial. Safety data will be monitored by this committee at 50% enrollment, and AEs will be reviewed by the DSMC during the meeting. The DSMC will review the event information and determine if any action is necessary. The DSMC may stop the study or put the study on hold pending further review.

### Ethical Considerations N/A

### Sharing of Results with Subjects N/A

**Funding Source:** We received a grant from Thrasher Foundation to support this study. We have also received iNO and placebo gas tanks for the study from Mallinckrodt Pharmaceuticals.

### Subject Stipends or Payments N/A

---

Current Version 9/10/2020 IRBNet #: 1170748  
Date:

Previous Version Page 23 of 25  
Date:

# Publication Plan

At the completion of the trial, we will prepare an abstract for presentation at a national pediatric meeting and then a manuscript will be prepared for submission to a peer review journal.

